#### 4.3.3.2.4. Gastric Ulcers and H. Pylori treatment

For the purposes of this study, a *gastric ulcer* is defined as a gastric lesion  $\geq 5$ mm in diameter with unequivocal depth by endoscopy.

A gastric ulcer is defined as *endoscopically significant* if it is  $\geq 3$ cm in length and  $\geq 1$ cm in width. Dimensions should be confirmed by capturing clear images with an accessory of known dimensions next to the lesion.

Gastric ulcers/gastritis require biopsy for H.pylori (urease test) and treatment with “triple” regimen for 14 days if positive.

- PPI BID
- Amoxicillin 1 gram PO BID
  - (Pcn allergic – substitute metronidazole 500 mg PO BID)
- Clarithromycin 500 mg PO BID

Blood hemoglobin will be monitored during scheduled or unscheduled endoscopies in patients who have ulcers or report signs of upper GI bleeding (hematemesis or melena).

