### Gastric Ulceration

Subjects who present with an endoscopically confirmed gastric ulcer will be treated as follows:

- **Ulcers whose smallest dimension (S) is  $\geq 2$ cm, or if there are any stigmata of increased risk of bleeding, such as visible vessels or clots**

The balloon should be extracted. Biopsy for H.pylori will be performed and treatment prescribed if positive.

These subjects should be treated with the following regimen: with sucralfate 1,000 mg PO Qid, and PPI medication twice daily for 3 months, followed by endoscopic evaluation after 3 months to confirm healing.

- **Ulcers whose smallest dimension (S) is  $\geq 1$  cm and  $< 2$  cm**

The balloon volume should be decreased by 150 ml (or 100 ml if starting volume is 400 ml) and subjects should be treated with the following regimen: sucralfate 1,000 mg PO Qid and increasing PPI medication to twice daily for 2 months. A biopsy for H.pylori will be taken and treatment prescribed if positive.

Endoscopic follow up will be performed at 8 weeks and if not healed at 8 weeks, an additional endoscopy at 16 weeks to confirm healing.

- At the 8-week follow-up, if signs of healing defined by a 25% reduction in either length or width are not observed, then the balloon should be extracted.
- At the 16-week follow-up, if signs of healing defined by a 50% reduction from baseline in either length or width are not observed, then the balloon should be extracted, and healing confirmed at follow up endoscopy 2-3 months after extraction.

These subjects will not undergo adjustment at  $18 \pm 4$  weeks.

- **Ulcers whose largest dimension is  $\geq 1$  cm and whose smallest dimension (S) is  $< 1$  cm.**

The balloon volume should be decreased by 150 ml (or 100 ml if starting volume is 400 ml) and subjects should be treated with the following regimen: sucralfate 1,000 mg PO Qid and increasing PPI medication to twice daily for 3 months. A biopsy for H.pylori will be taken and treatment prescribed if positive.

Endoscopic follow up will be performed at 12 weeks and if not healed at 12 weeks, an additional endoscopy at 20 weeks to confirm healing.

- At the 12-week follow-up, if signs of healing defined by a 25% reduction in either length or width are not observed, then the balloon should be extracted.
- At the 20-week follow-up, if signs of healing defined by a 50% reduction from baseline in either length or width are not observed, then the balloon should be extracted.

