### *4. 18- week adjustment*

At 18 weeks ± 4 weeks, all treatment arm subjects whose balloon has not been removed will be evaluated to determine if an upward adjustment is clinically appropriate. The following algorithm will be followed:

1. Subjects who have reached goal weight (calculated by BMI of 25) **and** are without any symptoms of gastroesophageal reflux or symptoms suggestive of gastritis or gastric ulcer, will not receive a balloon volume adjustment, and endoscopy at 18± 4 weeks will not be performed.
2. Subjects who underwent a prior unscheduled endoscopy with findings of a gastric ulcer will not receive an adjustment at 18± 4 weeks and no additional endoscopy beyond that described in section 2 above will be performed.
3. For all other subjects, endoscopy will be performed, and adjustments/treatment decisions will reflect the following algorithm:
  - a. For subjects with gastric ulceration found at endoscopy, **no upward adjustment** and PI will decide if balloon requires extraction based on endoscopic findings as described below.

Subjects who present with an endoscopically confirmed gastric ulcer will be treated as follows:

- **Ulcers whose smallest dimension (S) is  $\geq 2$ cm, or if there are any stigmata of increased risk of bleeding, such as visible vessels or clots**

The balloon should be extracted. Biopsy for H.pylori will be performed and treatment prescribed if positive.

These subjects should be treated with the following regimen: with sucralfate 1,000 mg PO Qid, and PPI medication twice daily for 3 months, followed by endoscopic evaluation after 3 months to confirm healing.

- **Ulcers whose smallest dimension (S) is  $\geq 1$  cm and  $< 2$  cm**

The balloon volume should be decreased by 150 ml (or 100 ml if starting volume is 400 ml) and subjects should be treated with the following regimen: sucralfate 1,000 mg PO Qid and increasing PPI medication to twice daily for 2 months. A biopsy for H.pylori will be taken and treatment prescribed if positive.

Endoscopic follow up will be performed at 8 weeks and if not healed at 8 weeks, an additional endoscopy at 16 weeks to confirm healing.

- At the 8-week follow-up, if signs of healing defined by a 25% reduction in either length or width are not observed, then the balloon should be extracted.

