- At the 16-week follow-up, if signs of healing defined by a 50% reduction from baseline in either length or width are not observed, then the balloon should be extracted, and healing confirmed at follow up endoscopy 2-3 months after extraction.

- **Ulcers whose largest dimension is  $\geq 1$  cm and whose smallest dimension (S) is  $< 1$  cm.**

The balloon volume should be decreased by 150 ml (or 100 ml if starting volume is 400 ml) and subjects should be treated with the following regimen: sucralfate 1,000 mg PO Qid and increasing PPI medication to twice daily for 3 months. A biopsy for H.pylori will be taken and treatment prescribed if positive.

Endoscopic follow up will be performed at 12 weeks and if not healed at 12 weeks, an additional endoscopy at 20 weeks to confirm healing.

- At the 12-week follow-up, if signs of healing defined by a 25% reduction in either length or width are not observed, then the balloon should be extracted.
- At the 20-week follow-up, if signs of healing defined by a 50% reduction from baseline in either length or width are not observed, then the balloon should be extracted.

These recommendations are summarized in the following table:

		L – Largest Dimension (cm)				
		0 – 0.5	0.5 – <1.0	1 – <2	2 – <3	≥ 3
S - Smallest Dimension (cm)	0 – 0.5	Not ulcer	Increase Medication	Decrease balloon volume Follow-up 12 and 20 weeks	Decrease balloon volume Follow-up 12 and 20 weeks	Decrease balloon volume Follow-up 12 and 20 weeks
	0.5 - <1		Increase Medication	Decrease balloon volume Follow-up 12 and 20 weeks	Decrease balloon volume Follow-up 12 and 20 weeks	Decrease balloon volume Follow-up 12 and 20 weeks
	1 - <2			Decrease balloon volume Follow-up 8 and 16 weeks	Decrease balloon volume Follow-up 8 and 16 weeks	Decrease balloon volume Follow-up at 8 and 16 weeks*
	≥ 2				Remove Device	Remove Device*

\*Endoscopically Significant

All subjects in whom a gastric ulcer is confirmed will have endoscopic confirmation of complete healing 2-3 months after the balloon extraction.

Erosive gastritis, and Small Ulcers

Subjects with ulcers < 1 cm in diameter in all dimensions (< 0.5 cm is not considered an ulcer) and erosive gastritis should be treated with the following regimen: sucralfate 1,000 mg PO Qid and increasing PPI medication to twice daily for 3 months. A biopsy for H.pylori will be taken and treatment prescribed if positive. Balloon volume reduction at the discretion of the PI.

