#### 4.4. Participant Retention

All patients will be encouraged to complete study follow-up, and all reasonable efforts will be made to ensure completeness of follow-up

It is understood that study participants may withdraw consent for study participation at any time irrespective of their reasons. The investigators may also withdraw a recipient from the study in order to protect their safety and/or if they are unwilling or unable to comply with the required study procedures.

In the event of a patient withdrawing from the trial, the reason for withdrawal must be documented on the CRF.

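### At the ulcer follow-up endoscopies a fall in one dimension alone counts as healing, so an ulcer that has grown overall can miss the extraction trigger (minor safety wording)

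*Combined protocol and SAP*

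**What the plan says.** Section 4.3.3.2.5, item 2 (unscheduled endoscopy, Gastric Ulceration) sorts ulcers by largest dimension (L) and smallest dimension (S).

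- S of 2 cm or more, or bleeding stigmata: remove the balloon.
- S from 1 to below 2 cm: reduce the volume, treat, re-scope at 8 weeks and, if unhealed, at 16 weeks.
- L of 1 cm or more with S below 1 cm: the same approach, with looks at 12 and 20 weeks.

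Each look carries an extraction trigger. The first is "At the 8-week follow-up, if signs of healing defined by a 25% reduction in either length or width are not observed". Item 4 of the same section (18-week adjustment, step 3a) repeats the scheme: "if signs of healing defined by a 25% reduction in either length or width are not observed, then the balloon should be extracted", then "At the 12-week follow-up, if signs of healing defined by a 25% reduction in either length or width are not observed", and for the later looks "if signs of healing defined by a 50% reduction from baseline in either length or width are not observed".

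Section 4.3.3.2.4 adds a size class: "A gastric ulcer is defined as *endoscopically significant* if it is" at least 3 cm long and at least 1 cm wide. It also says how size is recorded: "Dimensions should be confirmed by capturing clear images with an accessory of known dimensions next to the lesion". The table in section 4.3.3.2.5 stars the cells with L of 3 cm or more and S of 1 cm or more as endoscopically significant, which implies that length means L and width means S.

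**The concern.** The check is the scheduled test of whether a treated ulcer is improving enough for the balloon to stay. It can be passed on one dimension alone. No section sets a condition on the other dimension, on overall size or on depth at these looks. Read literally, an ulcer that has become larger overall can be recorded as showing signs of healing, including one that has become endoscopically significant since the previous look.

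The scheduled looks carry weight here. Under item 4, step 2, a subject with an ulcer at an earlier unscheduled endoscopy gets no 18-week endoscopy, so the item 2 checks are that subject's only scheduled looks before extraction. At stake is a delayed extraction in the occasional subject.

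**Working it through.** The plan gives no figure of its own to reproduce. The thresholds (25% and 50%), the look times (8/16 and 12/20 weeks), the 18 ± 4 week window and the size classes are from sections 4.3.3.2.4 and 4.3.3.2.5. Planned extraction at week 32 is from section 3.3. The ulcer dimensions below are illustrative assumptions, because the documents give no distribution of sizes.

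**Break-even growth.** If one dimension falls by a fraction r, length x width rises once the other grows by more than 1/(1 − r) − 1.
- 25% checks: 1/0.75 − 1 = 33.3%.
- 50% checks: 1/0.50 − 1 = 100%.

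**Examples (L x S, cm).** All pass the stated check, and S stays below 2 cm.

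| Check | Before | After | Change in L | Change in S | Product |
|---|---|---|---|---|---|
| 25% | 4.0 x 1.0 | 3.0 x 1.9 | −25% | +90% | 4.00 to 5.70 (+42.5%) |
| 25% | 3.0 x 0.8 | 2.2 x 1.2 | −26.7% | +50% | 2.40 to 2.64 (+10%) |
| 25% | 2.0 x 1.6 | 3.0 x 1.2 | +50% | −25% | 3.20 to 3.60 (+12.5%) |
| 50% | 2.0 x 1.5 | 4.2 x 0.75 | +110% | −50% | 3.00 to 3.15 (+5%) |

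The third ulcer was not endoscopically significant before and is now. Re-applying the size table at follow-up, which the plan does not say is done, would not remove any of these balloons: S of 2 cm or more is never reached, and L of 3 cm or more with S from 1 to below 2 cm calls only for a volume decrease.

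**Shape limit.** When length is the dimension that shrinks, the new width must exceed S/0.75 for the product to grow and cannot exceed 0.75 L. Baseline L/S must therefore exceed 1/0.75² = 1.78 at the 25% checks, and 1/0.5² = 4 at the 50% checks. When width shrinks there is no such limit. These limits rest on length meaning L and width meaning S; the break-even growth does not.

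**Time at stake.** Weeks from a passed 25% check to the next scheduled look or to week 32, for an ulcer found at week w:
- 8-week check: min(w + 16, 32) − (w + 8). This gives 8 weeks for w up to 16, 7 at w = 17 and 2 at w = 22.
- 12-week check: min(w + 20, 32) − (w + 12). This gives 8 weeks for w up to 12, 6 at w = 14, 1 at w = 19 and none from w = 20.

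**The 50% checks in item 4.** Ulcers are found there at weeks 14 to 22. The 16-week look then falls at week 30 or later (14 + 16), leaving at most 2 weeks, and the 20-week look at week 34 or later (14 + 20), after planned extraction. The 50% gap therefore matters mainly under item 2, for ulcers found early.

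**The case against.** The strongest reply is that the rule is a floor. It says when the balloon should come out and nowhere says it must otherwise stay. Investigators may scope at any time. At the 18-week visit "PI will decide if balloon requires extraction based on endoscopic findings as described below", and under section 4.4 "The investigators may also withdraw a recipient from the study in order to protect their safety". The DMC reviews safety and adjudicates events. A reader might infer that the plan obliges sites to leave a balloon next to a growing ulcer; the documents do not support that. What remains is that these protections are discretionary, and the 18-week decision points back to the same written criteria. They reduce the impact without correcting the criterion.

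Second, length x width is not a measure the protocol uses, and size-based removal depends on S alone. A newly found 3.0 x 1.2 cm ulcer would keep its balloon under the table, and the 4.0 x 1.0 cm example stays in its cell. A reader might also infer that becoming endoscopically significant breaches a removal rule; it does not, because that class triggers removal nowhere. This is fair and keeps the point minor. But the follow-up check asks a different question from the table, namely whether a treated ulcer is improving, and overall enlargement is a poor basis for answering yes.

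Third, one dimension must shrink by a quarter while the other grows by more than a third, despite a reduced volume, a twice-daily PPI and sucralfate. No document figure suggests that this is common, and it is probably rare.

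Fourth, a product condition alone would miss 2.0 x 1.9 to 3.0 x 1.2 cm, where the product falls from 3.80 to 3.60 but the ulcer becomes endoscopically significant. That stands, and the fix needs a clause for it.

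**Conclusion.** The gap in the wording is real and minor. At the 8- and 12-week checks, an ulcer with S below 2 cm and no bleeding stigmata can grow overall, with the other dimension up by more than 33%, and not meet the extraction trigger. The time at stake is at most 8 weeks to the next scheduled look or planned extraction, and less for most ulcers found at the 18-week visit. At the 50% checks the gap needs more than a doubling and has little practical reach.

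This rests on a literal reading, on illustrative ulcer sizes and, for the shape limits, on length and width meaning L and S. The frequency cannot be derived from the documents.

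A reader might take this as a threat to the efficacy result or to the gastric ulcer stopping rule. Neither follows. The gap changes no endpoint, estimate or error rate, and the stopping rule in section 6.3.2 counts lesions of 5 mm or more whether or not they later heal. This is a cheap improvement and not a required correction.

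**What to change.** In both items 2 and 4 of section 4.3.3.2.5, define signs of healing as: *at least a 25% [50%] reduction from baseline in length (largest dimension) or width (smallest dimension), with length x width not greater than at baseline and the ulcer not newly endoscopically significant.* Add: *the removal rule (smallest dimension 2 cm or more, or bleeding stigmata) applies at every follow-up endoscopy.*

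All four tabulated ulcers, and 2.0 x 1.9 to 3.0 x 1.2 cm, would then trigger extraction. A clearly shrinking ulcer with a trivial increase in one dimension keeps its balloon: 2.0 x 1.2 to 1.3 x 1.25 cm has length down 35% and product 2.40 to 1.625 (−32.3%). An ulcer with an unchanged product can still pass, for example 3.0 x 1.2 to 2.25 x 1.6 cm (3.60 both times). The clause rules out net growth and does not demand net shrinkage. The 50% edit in item 4 is mainly for consistency.

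The cost is wording in two places. Dimensions are already to be confirmed against an accessory of known size, so no new measurement is needed. There may be a few more early extractions, a number the documents do not allow to be estimated. Each is a sedated endoscopy with the tear and perforation risks in Table 1, although every balloon is due out at week 32 anyway. Under section 7.1.2 a subject explanted early is handled as a dropout and later weights are imputed.

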### Esophagitis

Subjects who present with esophagitis will be treated as follows:

- For subjects with esophagitis grade 3 or 4 at endoscopy, the balloon will be extracted, with the following medication regimen given:
  - Increase PPI to BID
  - Add Reglan 10 mg ac and Qhs
  - Add Gaviscon or Maalox 30 ml Q4h prn
  - Add Sucralfate Suspension 1,000 mg PO QID

Endoscopic evaluation will be conducted after 3 months to confirm healing.

- For subjects with esophagitis grade 1 or 2 at endoscopy, the balloon may be left in place, with the following medication regimen given for 2-3 months:
  - Increase PPI to BID
  - Add Reglan 10 mg ac and Qhs
  - Add Gaviscon or Maalox 30 ml Q4h prn
  - Add Sucralfate Suspension 1,000 mg PO QID

Endoscopic follow-up of these subjects prior to the 8-month extraction is not needed if they are asymptomatic. These subjects will not undergo adjustment at 18±4 weeks.

### *3. Early Adjustments for lack of effect*

For patients without any balloon effect from days 4-14 after the implantation, defined as lacking all of the following symptoms - nausea, vomiting, abdominal pressure, post prandial fullness, abdominal pain, heartburn, and eructation - an additional 250 ml will be added to the balloon.

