## 2. *Unscheduled endoscopy*

An unscheduled endoscopy may be performed at any time at the discretion of the investigator.

The following procedures will be applied to subjects who present with endoscopic findings based on an unscheduled endoscopy.

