These subjects will not undergo adjustment at 18±4 weeks.

These recommendations are summarized in the following table:

		L – Largest Dimension (cm)				
		0 – 0.5	0.5 – <1.0	1 – <2	2 – <3	≥ 3
S - Smallest Dimension (cm)	0 – 0.5	Not ulcer	Increase Medication	Decrease balloon volume Follow-up 12 and 20 weeks	Decrease balloon volume Follow-up 12 and 20 weeks	Decrease balloon volume Follow-up 12 and 20 weeks
	0.5 - <1		Increase Medication	Decrease balloon volume Follow-up 12 and 20 weeks	Decrease balloon volume Follow-up 12 and 20 weeks	Decrease balloon volume Follow-up 12 and 20 weeks
	1 - <2			Decrease balloon volume Follow-up 8 and 16 weeks	Decrease balloon volume Follow-up 8 and 16 weeks	Decrease balloon volume Follow-up at 8 and 16 weeks*
	≥ 2				Remove Device	Remove Device*

\*Endoscopically Significant

All subjects in whom a gastric ulcer is confirmed will have endoscopic confirmation of complete healing 2-3 months after the balloon extraction.

Erosive gastritis, and Small Ulcers

Subjects with ulcers < 1 cm in diameter in all dimensions (< 0.5 cm is not considered an ulcer) and erosive gastritis should be treated with the following regimen: sucralfate 1,000 mg PO Qid and increasing PPI medication to twice daily for 3 months. A biopsy for H.pylori will be taken and treatment prescribed if positive. Balloon volume reduction at the discretion of the PI.

Endoscopic follow-up of these subjects prior to the 8-month extraction is not needed if they are asymptomatic. These subjects will not undergo adjustment at 18±4 weeks.

Non-Erosive Gastritis

If non-erosive gastritis is found at endoscopy, subjects will be treated with increasing PPI medication to twice daily for 2 months. A biopsy for H.pylori will be performed and treatment prescribed if positive.

Endoscopic follow up and healing confirmation (and H.pylori eradication, if positive) will be deferred until the adjustment endoscopy at week 18±4 weeks or extraction endoscopy at 8 months, whichever comes first (must be at least 2 months after this unscheduled endoscopy), unless symptomatic.

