Endoscopic follow-up of these subjects prior to the 8-month extraction is not needed if they are asymptomatic.

- b. For subjects with Esophagitis grade 3 or 4, the balloon will be extracted, with the following medication regimen given for 3 months:
  - Increase PPI to BID
  - Add Reglan 10 mg ac and Qhs
  - Add Gaviscon or Maalox 30 ml Q4h
  - Add Sucralfate Suspension 1,000 mg PO QID

Endoscopic evaluation after 3 months to confirm healing.

- c. For subjects with esophagitis grade 1 or 2, no volume addition is given and the balloon may be left in place, with the following medication regimen given for 2-3 months:

- Increase PPI to BID
- Add Reglan 10 mg ac and Qhs
- Add Gaviscon or Maalox 30 ml Q4h prn
- Add Sucralfate Suspension 1,000 mg PO QID

If asymptomatic, endoscopic follow-up deferred until the extraction endoscopy at 8 months.

- d. For subjects with non-erosive gastritis found at endoscopy, balloon volume addition can be performed as per parameters below. These subjects will be treated with increasing PPI medication to twice daily for 2 months. A biopsy for H.pylori will be performed and treatment prescribed if positive. Endoscopic follow up and healing confirmation (and H.pylori eradication, if positive) deferred until the extraction endoscopy at 8 months, unless symptomatic.
4. For subjects without gastric ulceration, erosive gastritis or esophagitis (any grade), the following volume addition parameters should be followed:
- No addition for GE reflux symptoms not controlled by medication
  - 200 ml for subjects who previously received down adjustment for intolerance, but are currently asymptomatic
  - 200 ml for any height with GE reflux symptoms controlled by medication
  - 250 ml for height < 64 inches without GE reflux symptoms
  - 300 ml for height  $\geq$  64 inches without GE reflux symptoms

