**Note: The Maximum final volume of the balloon must not exceed 1,000 ml.**

Subjects who received an additional 250 ml in the first month for lack of any balloon effect will undergo an 18-week adjustment; however, their maximum final volume cannot exceed 1,000 ml. For example, a subject who started with 550 ml and then received 250 ml addition after 2 weeks due to lack of effect, cannot receive more than 200 ml addition at 18 weeks even if they do not have GE reflux symptoms and are  $\geq$  64 inches.

5. *Adjustment procedure*

The balloon adjustment procedure is done with an endoscopy procedure under the same sedation as the implantation procedure.

The adjustment procedure requires the patient to be on the following dietary restrictions:

- 72 hours prior to the procedure: Soft food only, no meat or vegetables in any form.
- 48 hours prior to the procedure: Full liquids only.
- 24 hours prior to the procedure: Clear liquids only.
- 12 hours prior to the procedure: No food or liquids by mouth.

The adjustment procedure is performed under conscious sedation by the anesthetist similar to the implantation procedure. The endoscope is introduced in the usual manner. The capped valve is identified and the suture loop is grasped with a standard rat tooth grasping forceps. The scope and cap are pulled out of the mouth, (the inflation tube stretches and reaches the mouth – see section 5.1) wherein the cap is twisted off and replaced with the extension tube (provided). The extension tube is lowered down the throat into the esophagus followed by the scope. The adjustment commences by utilizing the 3-way stopcock on the proximal end of the extension tube. Following completion of the adjustment, the extension tube is pulled out of the mouth and is replaced by the cap. The cap is lowered back into the throat and allowed to pull itself back to its position touching the white catheter. The scope then pushes it down into the stomach.

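### The early 250 ml balloon addition is ordered on absence of symptoms alone, without the endoscopic condition that the protocol applies to the 18-week addition

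*Combined protocol and SAP*

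**What the plan says.** All of this is in Section 4.3.3.2.5 (Adjustments) of the protocol unless noted.

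- **Item 3, early adjustment.** The trigger is the absence of every listed symptom (nausea, vomiting, abdominal pressure, fullness after meals, abdominal pain, heartburn, eructation) from days 4 to 14. The action is mandatory: "an additional 250 ml will be added to the balloon". No endoscopic finding is mentioned.
- **Item 5, procedure.** "The balloon adjustment procedure is done with an endoscopy procedure under the same sedation as the implantation procedure". This is general wording, so it covers the early adjustment too.
- **Item 4, 18-week adjustment.** Step 4 limits who may receive volume: "For subjects without gastric ulceration, erosive gastritis or esophagitis (any grade), the following volume addition parameters should be followed". Step 3a rules out an upward adjustment with ulceration and step 3c rules out an addition with grade 1-2 esophagitis. Step 3d leaves one finding outside the bar: "For subjects with non-erosive gastritis found at endoscopy, balloon volume addition can be performed as per parameters below".
- **Note under item 4.** Subjects who had the early addition are held to a final volume of 1,000 ml. That limits volume and says nothing about the mucosa.
- **Item 2, unscheduled endoscopy.** "The following procedures will be applied to subjects who present with endoscopic findings based on an unscheduled endoscopy". For ulcers under 1 cm and erosive gastritis it prescribes medication and adds: "Balloon volume reduction at the discretion of the PI". For these findings and for grade 1-2 esophagitis, the only upward adjustment it withholds is the later one: "These subjects will not undergo adjustment at 18±4 weeks".

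**The concern.** The two upward adjustments are alike in size and method, but only the later one depends on what the endoscopist sees. An investigator who finds a small ulcer, erosive gastritis or mild esophagitis at the early adjustment, and who follows item 3 exactly, adds 250 ml onto a lesion for which the same protocol withholds volume at 18 weeks. An investigator who sensibly holds back departs from a mandatory instruction.

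What is at stake is the safety of a small number of subjects and consistent conduct across up to 10 centers. No effect on the co-primary endpoints or on the gastric ulcer rate reviewed by the Data Monitoring Committee is claimed.

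**Working it through.** The plan states no figure to reproduce here. The check sets the rules side by side and then does simple volume arithmetic.

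**Rules by finding** (items 2, 3 and 4)

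| Finding | Item 2, if the early endoscopy counts as unscheduled | Item 3, early addition | Item 4, 18-week addition |
|---|---|---|---|
| Ulcer with smallest dimension 2 cm or more, or signs of bleeding risk | Extract | 250 ml, no condition stated | No; extract |
| Other ulcer with largest dimension 1 cm or more | Reduce by 150 ml (100 ml if started at 400 ml) | 250 ml, no condition stated | No; reduce |
| Esophagitis grade 3-4 | Extract | 250 ml, no condition stated | No; extract |
| Ulcer under 1 cm in all dimensions, without signs of bleeding risk | Medication; reduction optional; 18-week adjustment barred | 250 ml, no condition stated | No |
| Erosive gastritis | Medication; reduction optional; 18-week adjustment barred | 250 ml, no condition stated | No |
| Esophagitis grade 1-2 | Medication; 18-week adjustment barred | 250 ml, no condition stated | No |
| Non-erosive gastritis | Medication | 250 ml, no condition stated | Allowed |

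In the first three rows, item 2 conflicts with item 3 and would sensibly prevail, although no sentence says that the early endoscopy is unscheduled or that item 2 overrides item 3. In the next three rows there is no conflict to resolve: item 2 does not withhold the early addition, while item 4 withholds the later one. These three rows are the gap.

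**Volumes.** Starting volumes are from Section 4.3.3.2.1 (Implantation).

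| Start (ml) | Start + 250 (ml) | 250 / start |
|---|---|---|
| 400 | 650 | 62.5% |
| 450 | 700 | 55.6% |
| 500 | 750 | 50.0% |
| 550 | 800 | 45.5% |

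The 18-week additions, which do carry the condition, are 200-300 ml.

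**Other limits.** Every result, 650-800 ml, is under the 1,000 ml cap. Each is also under the threshold in item 6, which requires a mucosal check 4 weeks later only above 900 ml. Neither limit stands in for a mucosal condition. If the early endoscopy is unscheduled, item 2 asks for no endoscopic follow-up of a small ulcer before the 8-month extraction when the subject is asymptomatic, and item 4, step 2 removes the 18-week endoscopy for subjects with an earlier ulcer. A silent small ulcer could then carry the extra volume until extraction with no planned look in between.

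**How many subjects.** The documents give neither the rate of early additions nor the rate of lesions at that endoscopy. Both are assumed here at 5-10%, with 188 subjects randomized to the device (Section 7.2):

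- Low: 188 × 0.05 × 0.05 = 0.47
- High: 188 × 0.10 × 0.10 = 1.88

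The count is lower if not all 188 are implanted.

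**The case against.** The best reply is that item 2 already governs. The only adjustment scheduled by time is the one at 18 weeks, so an endoscopy in the first weeks is naturally unscheduled. On that reading the serious lesions lead to reduction or extraction. For small ulcers and erosive gastritis, item 2 orders three months of intensified treatment and permits a reduction, so inflating in the same session would run against its sense. Section 1.5.2 also makes the investigator responsible for subject safety. On this view the text is silent between two items and does not instruct anyone to inflate onto a lesion.

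The situation should also be rare. The implantation endoscopy excludes these findings, and all device subjects take a daily acid suppressant. Section 3.5.2 excludes subjects positive for H. pylori and those on daily gastric irritants or corticosteroids. Item 3 itself requires the absence of heartburn and abdominal pain. A follow-up appointment comes 1-2 weeks after an adjustment (Section 4.3.4), and volume can be reduced at any time for persistent symptoms (item 1).

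Most of this stands and limits the weight of the point. It confines the gap to the smaller lesions and makes it uncommon. It does not close it. The discretion in item 2 concerns reducing volume and is not offered at all for grade 1-2 esophagitis. No sentence withholds the early addition. The follow-up appointment and item 1 depend on symptoms, so they would miss a silent lesion. The protocol does not itself treat absence of symptoms as proof of a healthy mucosa: at 18 weeks it still sends nearly all subjects without an earlier ulcer to endoscopy, and item 2 makes provision for asymptomatic subjects with these lesions.

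**Conclusion.** The concern holds. Item 3 orders the early addition on symptoms alone. For ulcers under 1 cm, erosive gastritis and grade 1-2 esophagitis, nothing elsewhere withholds it, although each of these findings bars volume at 18 weeks. For larger ulcers and grade 3-4 esophagitis the natural reading of item 2 already protects the subject, and only an explicit link is missing.

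The consequence is a balloon of 650-800 ml where 400-550 ml would be kept if the addition were withheld. The estimate of about 0.5 to 1.9 subjects rests wholly on the assumed rates. That the text lacks the condition is certain. How often volume would in fact be added onto a lesion is not known from the documents. This is a minor safety correction that should be made. Power, sample size and the analyses are unaffected.

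**What to change.** Add one sentence to item 3: the 250 ml is not added if endoscopy shows gastric ulceration, erosive gastritis or esophagitis of any grade, and such findings are managed under item 2. This carries over the protocol's own 18-week condition and settles how items 2 and 3 relate. Non-erosive gastritis stays outside the bar, in line with item 4, step 3d.

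The cost is one sentence in an amendment. The endoscopy is already part of the adjustment, so no procedure is added. A few subjects would forgo the early addition. Because item 2 also withholds the 18-week adjustment for these findings, they would receive neither upward adjustment. That second loss already follows from item 2 if the early endoscopy is read as unscheduled, so the sentence adds little to it.
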